## 10 TREATMENT

All patients will receive best available standard of care. Depending on the severity of COVID-19 and need for hospitalization, standard of care can include, but is not limited to, monoclonal antibody formulations directed against the SARS-CoV-2 Spike protein, remdesivir, dexamethasone, and tocilizumab. Treatment in the Main Cohort will consist of lead-in single agent rintatolimod (first 3 patients on the dose-escalation component) followed by the combination of rintatolimod and dose-escalation of rIFN $\alpha$ . Intravenous (IV) rintatolimod is administered as a fixed dose (200 mg per infusion) and IV rIFN $\alpha$  dose-escalation will be a standard 3 + 3 design, with the following doses per infusion: 0, 5, 10, and 20 MU/M $^2$ . The dose-escalation phase will lead to which patients will receive IFN $\alpha$  at 20 MU/M $^2$  or at MTD + rintatolimod (200 mg). The regimen will be administered on Day 1 and on Day 3 (or 4), and EOT assessments will occur on Day 7 ( $\pm$  1 day) and Day 14 ( $\pm$  3 days). This portion of the study will allow for additional safety data and the analysis of the effect of the study regimen on nasopharyngeal viral load. Using each patient's baseline nasopharyngeal viral load, we will evaluate to what extent the study regimen reduces viral load relative to supportive care only.

Treatment in the Expansion Cohort will be IV rintatolimod is administered as a fixed dose (200 mg per infusion on Day 1 and on Day 3 (or 4). Based on the PI's judgment, additional infusions of rintatolimod at 200 mg may be administered 3 to 4 days apart. Decisions about additional rintatolimod infusions will be based on evaluation of AEs attributed to rintatolimod, particularly increased FIO $_2$  needs. A maximum of 12 rintatolimod infusions may be administered per patient. The rationale for a maximum of 12 infusions was based on discussions with leadership from AIM Immunotech regarding the expected effects of rintatolimod on innate immune responses over time based on data from patients with and without cancer. Rintatolimod activates innate immune responses through a number of mechanisms including activation of RNase L and inducing interferon stimulated genes (ISGs). Administration of rintatolimod over a number of weeks may be required for sustained activation of innate immune responses to clear SARS-CoV-2.

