### 10.1 Dosing and Administration

#### Interferon-Enhancing Regimen

For dosing, refer to **Table 1**. The regimen will be administered on Days 1 and 3 (or 4) in the following order:

- Pretreatment: 500 mL Normal saline IV over 60 minutes
- Pre-medications: acetaminophen (Tylenol®) 650 mg by mouth x 1 dose; prochlorperazine (Compazine®) 10 mg by mouth x 1 dose – administered 30 minutes ( $\pm$ 5 minutes) after starting pre-treatment hydration
- Interferon alpha-2b: (dose-escalation; maximum 20 MU/M $^2$ ) IV over 20 minutes

Rintatolimod: 200 mg IV, initial administration to start at 20 mL/ hour and increase to 40 mL/ hour after 30 minutes as per the standard at Roswell. Total duration of rintatolimod infusion: 2.5 h-3h. Tubing should be flushed with 30 to 50 mL of normal saline solution upon completion. Administration will be followed by 1 hour of observation and vital signs at 30 and 60 minutes post-infusion ( $\pm$  5 minutes).

Roswell Park Protocol No.: I-659920

Pretreatment and pre-meds listed above are recommendations and may be modified based upon institutional SOC requirements and at the discretion of the investigator. Treatment can be administered in the outpatient or inpatient setting, per the investigator's/physician's discretion.

Each daily treatment will be initiated after interval history and physical examination is performed and once the relevant laboratory studies have been confirmed to be within clinically acceptable ranges, specifically: ANC  $\geq$  1000/mm^3, total bilirubin  $\leq$  3x ULN, AST and ALT  $\leq$  5 x ULN.

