#### **10.2 Dose Modification**

Based on our experience with the combination of rintatolimod and INTRON® A as anti-cancer treatment (over longer periods of time than the currently proposed trial for COVID-19), we do not expect the need for dose modifications. However, in case of specific toxicities, dose modification rules will be used (**Table 2**). Taking into account that the rationale for the regimen is a short-term intervention to augment antiviral immunity for an acute viral infection, we do not plan for re-escalations or administration of any missing doses after successful management of toxicities. Since the progression of COVID-19 is believed to be facilitated by lack of the activation of innate immunity (IFN responses and RNases), we anticipate that even transient (or lower intensity) activation of these pathways may help to better control the viral spread. Toxicity will be assessed according to the NCI Common Terminology Criteria for Adverse Events Version 5.0 (CTCAE v5.0).

Therapy will be immediately discontinued for any grade IV treatment-related toxicity that becomes apparent. In the event of any adverse effect, appropriate medical treatment will be instituted and study treatment will be discontinued based on physician judgment.

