**Table 2 Treatment Related Toxicity Management**

Treatment-related AEs	Toxicity grade or conditions (CTCAE5.0)	Action taken for Interferon Alpha-2b	Action taken for Rintatolimod	Additional actions
Chills/Fever	Grade 3 that persists for $\geq$ 48 hours despite acetaminophen	None	None	Consider additional acetaminophen dosing, supportive care
Pancreatitis	Grade 3	Hold  Decreased future doses by 75% (to 5MU/M2)	Hold	Supportive measures as clinically indicated
AST / ALT elevation or Increased bilirubin	Grade 3	Hold until improved to grade 1; Decrease future doses by 75%	Hold	Advise evaluation for other possible etiologies; consider imaging
Vomiting	Grade 3 vomiting $\geq$ 48 hours despite optimal anti-emetic therapy	Hold until resolved to grade 1; Decrease future doses by 75%	Hold	
Depression or other clinically relevant mood disorder	Grade 3	Permanently discontinue; appropriate supportive care/intervention	None	Patients and family members will be informed in advance about the potential for depression and anxiety, including worsening of pre-existing mood disorders.
Neutropenia	Grade 3 or 4	If Grade 3, decrease future doses by 75%. If Grade 4, permanently discontinue	Hold	Transient neutropenia is expected as a result of neutrophil activation and redistribution rather than bone marrow suppression. Recent cytotoxic chemotherapy is an additional cause of neutropenia. COVID-19 is known to cause lymphopenia, but not neutropenia. For prolonged neutropenia that is not expected from the study regimen and recent chemotherapy (if applicable), the primary oncologist and a hematologist will be consulted.
Hemorrhage	Grade 2 or greater	None	None	
Myocardial infarction, stroke,		Permanently discontinue; appropriate	Permanently discontinue; appropriate	

Treatment-related AEs	Toxicity grade or conditions (CTCAE5.0)	Action taken for Interferon Alpha-2b	Action taken for Rintatolimod	Additional actions
or other arterial thrombotic event		supportive care/intervention	supportive care/intervention	
All other clinically significant AEs 	Intolerable Grade 2 or Grade 3	Hold therapy until resolved to Grade 1 or baseline; reduce future doses by 75%	Hold therapy until resolved to Grade 1 or baseline; reduce future doses by 50%	
	Grade 4	Permanently Discontinue	Permanently Discontinue	

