### 10.2.1 Interferon Alpha-2b and/or rintatolimod Non-hematologic toxicities

Considered to be possibly, probably, or definitely related to interferon alpha-2b and rintatolimod:

- **Interferon Alpha-2b:**

For grade 3 toxicity not addressed in Table 2:

- 1st episode: dose will be held and restarted at the next study visit at a dose reduction by 75%. The dose can be re-escalated if toxicity is reduced to ≤ grade 1 or baseline.
- 2nd episode: Treatment will be discontinued.

For grade 4 toxicity

- Treatment will be discontinued

Roswell Park Protocol No.: I-659920

- **Rintatolimod:**

For grade 3 toxicity not addressed in Table 2:

- 1st episode: dose will be held and restarted at the next study visit at a dose reduction by 50%. The dose can be re-escalated if toxicity is reduced to  $\leq$  grade 1 or baseline.
- 2nd episode: Treatment will be discontinued.

For grade 4 toxicity:

- Treatment will be discontinued

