### **19.7 Safety Review and Study Suspension**

The Roswell Park Data Safety and Monitoring Committee (DSMC) will assess the progress of the study, the safety data, and critical efficacy endpoints. The DSMC will review the study weekly and will make recommendations that include but not limited to; (a) continuation of the study, (b) modifications to the design (c) suspension of or, (d) termination of the study.

Additionally, should the study be suspended due to safety; members of the research team, study statistician, and DSMC will meet to discuss safety concerns and possible adjustments to the study or study closure.

Therapy will be discontinued for any Grade 4 treatment-related toxicity.

Roswell Park Protocol No.: I-659920

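### Table 2 lets dosing continue after grade 4 hemorrhage and only holds rintatolimod for grade 4 neutropenia, although sections 10.2 and 19.7 stop therapy for any grade 4 treatment-related toxicity

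*Combined protocol and SAP*

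**What the plan says.** The general rule appears twice. Section 10.2 says: "Therapy will be immediately discontinued for any grade IV treatment-related toxicity that becomes apparent". Section 19.7 says: "Therapy will be discontinued for any Grade 4 treatment-related toxicity". Neither carries an exception.

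Section 10.2.1, headed for non-hematologic toxicity, gives the same instruction at grade 4 for each drug separately: "Treatment will be discontinued". Its grade 3 instruction is introduced by "For grade 3 toxicity not addressed in Table 2"; the grade 4 instruction has no such limit.

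Table 2 manages treatment-related events drug by drug. Its hemorrhage row reads "Hemorrhage Grade 2 or greater None None", the two last entries being the actions for interferon and for rintatolimod. Its neutropenia row covers grades 3 and 4. The interferon entry separates the grades and ends the drug at grade 4. The rintatolimod entry is a single hold for both: "If Grade 4, permanently discontinue Hold Transient neutropenia is expected". A later row permanently stops both drugs at grade 4, but only for events that have no row of their own.

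**The concern.** The text and the table give different orders for the same patient. A clinician who follows the table after a grade 4 treatment-related bleed would give the next dose of both drugs; one who follows the text would stop. After grade 4 neutropenia, the table leaves rintatolimod open to resumption and the text does not.

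The conflict is confined to grade 4. Taking no action for grade 2 or 3 hemorrhage may be debatable clinically, but it does not breach the grade 4 rule and is not part of this point.

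What is at stake is patient safety. A bleed is foreseeable: section 13.1 lists low platelets with bruising or bleeding among the risks of interferon. Under section 10.2.2 a treatment-related grade 4 bleed within Days 1 to 7 would also be a dose-limiting toxicity, so the event could count against the dose level while the management table asks for no change to either drug.

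**Working it through.** There is no plan figure to reproduce. The check sets the rules side by side and then counts what follows from them.

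**1. Same events.** Sections 10.2 and 19.7 concern treatment-related toxicity at grade 4. Table 2 concerns treatment-related events on the same CTCAE scale, apart from cytokine release syndrome, which uses the Penn scale. The hemorrhage row reaches grade 4 because it has no upper limit; the neutropenia row names grade 4.

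**2. Action at grade 4.**

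| Event | Sections 10.2 and 19.7 | Table 2, interferon | Table 2, rintatolimod |
|---|---|---|---|
| Hemorrhage | Stop | No action | No action |
| Neutropenia | Stop | Permanent stop | Hold |

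Hemorrhage conflicts for both drugs. Neutropenia conflicts for rintatolimod only.

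**3. Does another clause resolve it?**
- The grade 4 row for all other events does not reach an event with its own row.
- In section 10.2.1 the grade 4 instruction does not give way to Table 2, because the limiter sits on grade 3 alone. That section adds to the conflict for hemorrhage, if hemorrhage is classed as non-hematologic.
- No order of precedence is stated.

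**4. Count of cells.** Five rows can apply at grade 4: neutropenia, hemorrhage, arterial thrombotic event (no grade stated), all other events at grade 4, and cytokine release syndrome.
- Cells: 5 rows × 2 drugs = 10.
- Not stopping the drug: 2 (hemorrhage) + 1 (neutropenia, rintatolimod) = 3.
- Stopping the drug: 10 − 3 = 7.

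This describes the table's wording and is not a measure of risk. The conflict does not depend on which rows are counted.

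**5. Doses still possible after a grade 4 event following dose 1.**
- Main Cohort, two planned doses (section 10.4): 2 − 1 = 1.
- Expansion Cohort, where "A maximum of 12 rintatolimod infusions may be administered per patient": 12 − 1 = 11, of which 1 is scheduled on Day 3 or 4 and 11 − 1 = 10 are optional.

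Both are ceilings, not expected numbers.

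**6. Where a hold differs from a stop.** In the Main Cohort, section 10.1 allows each treatment only "once the relevant laboratory studies have been confirmed to be within clinically acceptable ranges", including ANC of at least 1000/mm³, and section 10.2 plans no make-up of missed doses. A hold for grade 4 neutropenia is therefore nearly a stop there. That laboratory gate includes no platelet or bleeding criterion, so it does not cover hemorrhage. In the Expansion Cohort, the part of section 10.1 on that cohort does not repeat the ANC check, and sections 3.3 and 3.4 set no ANC or platelet floor for entry. Additional infusions there are new optional doses rather than missed ones, so the provision against making up doses does not clearly bar them.

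**The case against.** The best defence is that the stricter rule is already in force. It is unqualified, it is stated in two places, and section 10.2.1 repeats it for non-hematologic events. On that reading Table 2 governs dose changes below the ceiling and the general rule sets the ceiling. Section 10.2 also lets the physician stop treatment for any adverse effect.

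The practical exposure is also small. In the Main Cohort a hold works almost as a stop. The Expansion Cohort, where it does not, receives no interferon, the drug to which the protocol mainly attributes transient neutropenia and bleeding. For rintatolimod, section 13.2 reports no dose-limiting hematologic toxicity in over 800 patients. Blood counts are scheduled in that cohort, and the investigator weighs adverse events attributed to rintatolimod before each added infusion. Finally, the hold may be deliberate, because Table 2 explains the neutropenia as expected redistribution of cells.

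Most of this stands as a limit on frequency. It does not remove the contradiction. Section 10.2 itself directs the clinician to Table 2 for specific toxicities, and a specific row is commonly read as overriding a general sentence. Discretion to stop is weaker than an order to stop. The scheduled counts in the Expansion Cohort have no threshold attached. If the hold is deliberate, it is an exception that sections 10.2 and 19.7 do not admit.

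**Conclusion.** The concern holds. At grade 4, Table 2 contradicts sections 10.2 and 19.7 in three drug-action cells: hemorrhage for both drugs and neutropenia for rintatolimod. Hemorrhage is the more serious, because the table taken literally continues treatment. The neutropenia conflict matters mainly in the Expansion Cohort.

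The likely effect is small: few patients, at most 1 further dose in the Main Cohort and at most 11 in the Expansion Cohort. The documents give no rate of grade 4 hemorrhage or neutropenia with this regimen, so an expected number cannot be calculated. The conclusion assumes only that the event is judged treatment-related and that the table is read as printed. It should be corrected because the conflict concerns a life-threatening event and the correction is easy.

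**What to change.** Split the hemorrhage row so that grade 4 permanently discontinues both drugs. In the neutropenia row, divide the rintatolimod entry by grade, as the interferon entry already is, with permanent discontinuation at grade 4.

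If the sponsor wants rintatolimod to resume after transient grade 4 neutropenia, that exception should be written into both 10.2 and 19.7 with a resume criterion, for example the ANC of at least 1000/mm³ already used in 10.1, and stated to apply to the Expansion Cohort as well.

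The cost is one row split and one cell changed, or, for neutropenia, one sentence in each of the two sections if the exception is chosen. The DLT definition, endpoints, sample size and analysis are untouched. The downside of the stricter option is that a few patients with transient grade 4 neutropenia may lose later rintatolimod doses.

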**Table 2 Treatment Related Toxicity Management**

Treatment-related AEs	Toxicity grade or conditions (CTCAE5.0)	Action taken for Interferon Alpha-2b	Action taken for Rintatolimod	Additional actions
Chills/Fever	Grade 3 that persists for $\geq$ 48 hours despite acetaminophen	None	None	Consider additional acetaminophen dosing, supportive care
Pancreatitis	Grade 3	Hold  Decreased future doses by 75% (to 5MU/M2)	Hold	Supportive measures as clinically indicated
AST / ALT elevation or Increased bilirubin	Grade 3	Hold until improved to grade 1; Decrease future doses by 75%	Hold	Advise evaluation for other possible etiologies; consider imaging
Vomiting	Grade 3 vomiting $\geq$ 48 hours despite optimal anti-emetic therapy	Hold until resolved to grade 1; Decrease future doses by 75%	Hold	
Depression or other clinically relevant mood disorder	Grade 3	Permanently discontinue; appropriate supportive care/intervention	None	Patients and family members will be informed in advance about the potential for depression and anxiety, including worsening of pre-existing mood disorders.
Neutropenia	Grade 3 or 4	If Grade 3, decrease future doses by 75%. If Grade 4, permanently discontinue	Hold	Transient neutropenia is expected as a result of neutrophil activation and redistribution rather than bone marrow suppression. Recent cytotoxic chemotherapy is an additional cause of neutropenia. COVID-19 is known to cause lymphopenia, but not neutropenia. For prolonged neutropenia that is not expected from the study regimen and recent chemotherapy (if applicable), the primary oncologist and a hematologist will be consulted.
Hemorrhage	Grade 2 or greater	None	None	
Myocardial infarction, stroke,		Permanently discontinue; appropriate	Permanently discontinue; appropriate	

Treatment-related AEs	Toxicity grade or conditions (CTCAE5.0)	Action taken for Interferon Alpha-2b	Action taken for Rintatolimod	Additional actions
or other arterial thrombotic event		supportive care/intervention	supportive care/intervention	
All other clinically significant AEs 	Intolerable Grade 2 or Grade 3	Hold therapy until resolved to Grade 1 or baseline; reduce future doses by 75%	Hold therapy until resolved to Grade 1 or baseline; reduce future doses by 50%	
	Grade 4	Permanently Discontinue	Permanently Discontinue	
Cytokine Release Syndrome	≥ Grade 2, based on the Penn scale (45)	Permanently Discontinue	Permanently Discontinue	In discussion with the primary oncologist, tocilizumab, corticosteroids, and potentially other immunomodulators will be used based on clinical judgement for ARDS and CRS-like complications.

 Transient neutropenia is known to occur with rIFN- $\alpha$  and may reflect increased neutrophil migration to sites of infection or the tumor microenvironment as well as the effect of IFN- $\alpha$  on neutrophil survival and lifespan (46). This transient neutropenia has not been associated with an increased risk of infection.

 Refer to: <https://www.ncbi.nlm.nih.gov/pmc/articles/PMC5833070/> (Porter D, Frey N, Wood PA, Weng Y, Grupp SA. Grading of cytokine release syndrome associated with the CAR T cell therapy tisagenlecleucel [published correction appears in J Hematol Oncol. 2018 Jun 13;11(1):81]. J Hematol Oncol. 2018;11(1):35. Published 2018 Mar 2. doi:10.1186/s13045-018-0571-y].

### 10.2.1 Interferon Alpha-2b and/or rintatolimod Non-hematologic toxicities

Considered to be possibly, probably, or definitely related to interferon alpha-2b and rintatolimod:

- **Interferon Alpha-2b:**

For grade 3 toxicity not addressed in Table 2:

- 1st episode: dose will be held and restarted at the next study visit at a dose reduction by 75%. The dose can be re-escalated if toxicity is reduced to ≤ grade 1 or baseline.
- 2nd episode: Treatment will be discontinued.

For grade 4 toxicity

- Treatment will be discontinued

Roswell Park Protocol No.: I-659920

- **Rintatolimod:**

For grade 3 toxicity not addressed in Table 2:

- 1st episode: dose will be held and restarted at the next study visit at a dose reduction by 50%. The dose can be re-escalated if toxicity is reduced to  $\leq$  grade 1 or baseline.
- 2nd episode: Treatment will be discontinued.

For grade 4 toxicity:

- Treatment will be discontinued

#### **10.2.2 Definition of DLT**

Treatment-related DLTs will be defined as the following events that occur between Day 1 to Day 7 that are considered possibly, probably, or definitely treatment-related:

- Grade 4 hematologic toxicity.
- Grade 3 hematologic toxicity with exception of transient leukopenia, neutropenia, lymphopenia, thrombocytopenia without bleeding, or anemia lasting 7 days or less.
- Grade 4 non-hematologic toxicities, with exception of asymptomatic increased LDH or lipase or amylase.
- Grade 3 non-hematologic toxicities with exception of nausea, vomiting, diarrhea, or flu-like symptoms that are controlled by optimal supportive management.

Distinguishing clinical manifestations of COVID-19 from treatment-related DLT can be difficult because they can overlap. Manifestations of COVID-19 present at baseline (e.g., fever, shortness of breath) that are unchanged after the study regimen is begun will not be considered DLT. Worsening of these manifestations can be due to COVID-19 or treatment-related, and unless there is a specific well defined unrelated cause, all AEs that are at least possibly related to the study regimen that meet one of the criteria for DLT based on CTCAE severity will be considered DLT.

In patients who received recent chemotherapy, radiation, and/or immunotherapy toxicities from recent chemotherapy would be known to the primary oncologist, and we would interpret AEs attributed to the study regimen with this knowledge in mind. For example, if a patient received cytotoxic chemotherapy known to cause leukopenia prior to development of COVID-19, development of leukopenia following initiation of study therapy will not be considered treatment-related, depending on the expected degree and duration of leukopenia following chemotherapy.

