## 9 STUDY DESIGN

The antiviral efficacy of the combination of interferon alpha-2b and rintatolimod will be evaluated by administering fixed doses of each drug. Subjects will receive 1 day of the combination (Day 1), followed by 1 day of observation and the same regimen on Day 3 (or Day 4), according to the safe established dosing levels (see Table 1). During this time, subjects will be monitored continuously for safety (refer to Section 19.2.1). As the standard of care therapy for COVID-19 is evolving, all patients will receive optimal standard of care that will be administered concurrently with the study drug regimen. In a double-blind, randomized, multi-center, placebo-controlled trial of intravenous remdesivir in adults hospitalized with COVID-19 with evidence of lower respiratory tract involvement, remdesivir treatment resulted in shortening the time to recovery by 4 days (43). Though 14-day survival was greater in remdesivir recipients, the difference was not statistically significant (43). Adults hospitalized with COVID-19 with evidence of lower respiratory tract involvement will be offered remdesivir through an EUA if and when this drug is available to us. If we're not able to offer remdesivir to all patients based on drug availability, we expect a similar proportion of patients in the study drug and control arms to have received remdesivir, and the effect of remdesivir on study endpoints will be evaluated in an exploratory fashion.

Roswell Park Protocol No.: I-659920

In a multi-center controlled, open-label trial comparing a range of possible treatments in patients who were hospitalized with COVID-19, patients were randomly assigned to receive oral or intravenous dexamethasone (6 mg daily) for up to 10 days or to receive usual care alone (44). Overall, 482 patients (22.9%) in the dexamethasone group and 1110 patients (25.7%) in the usual care group died within 28 days after randomization ( $p < 0.001$ ). The survival benefit of dexamethasone was observed among patients receiving either invasive mechanical ventilation or oxygen alone at randomization but not among those receiving no respiratory support. Based on these results, dexamethasone (6 mg/day) will be given as standard of care to patients admitted with COVID-19 who require supplemental oxygen.

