## 19.2 Proposed Data Analysis

### 19.2.1 Safety

#### SAFETY RUN-IN DESIGN

We will use a 3+3 dose escalation scheme in order to determine the safe dose to utilize in our efficacy analysis. The 3+3 design will consider four dose levels of IFN $\alpha$  (0, 5 MU/M $^2$ , 10 MU/M $^2$  and 20 MU/M $^2$ ) and fixed dose rintatolimod (200 mg per day) administered on Days 1 and 3.

For each cohort, the given dose level will start with three patients, with three patients added to any dose level if we observe 1 out of 3 DLTs. The patients in each cohort will be staggered, so that the first patient in each cohort will have received treatment on Days 1 and 3 before the following patient(s) are enrolled in that cohort. If 2 out of 3 to 6 subjects have a DLT we will not proceed to the next dose level.

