## Appendix F

### Study Calendar (Main Cohort)

Baseline and/or Screening assessments must be performed within 3 days prior to the first dose of investigational product unless otherwise stated. Therapy may begin on the same day as screening. *If screening and day 1 are completed on the same day, then assessments required on both days may be done only once\**. Any results falling outside of the reference ranges may be repeated at the discretion of the investigator.

\*If screening and day 1 occur on the same day, correlative blood draw and nasopharyngeal swab collection will be as follows:

Correlative blood draw: In the case when day one of treatment is the same as the screening day, only two blood draws (30 mL each time) are needed for the correlative studies on that day: Before the start of treatment and within 1 hour after the end of the combined infusion (i.e., collect one pre-dose sample and one sample within one hour after end of rintatolimod IV, if screening and Day 1 are the same day).

Nasopharyngeal swabs: In the case when day one of treatment is the same as the screening day, only one nasopharyngeal swab (pre-dose) is required.

Evaluation	Screening and Informed Consent	Day 1	Day 3 (+ 1 day)	Day 7 (± 1 day) and Day 14 (± 3 days) 
Written Informed Consent prior to any Screening Procedures	X			
Recording of Concomitant Medications		X	X	X
Recording of Adverse Events		X	X	X
Survival Follow-up (through Day 14)		X	X	X
Clinical Assessments				
Medical & Surgical History		X		

Evaluation	Screening and Informed Consent	Day 1	Day 3 (+ 1 day)	Day 7 (± 1 day) and Day 14 (± 3 days)
Physical Exam including vital signs 	X	X	X	X
ECOG Performance Status	X	X	X	X
Laboratory Procedures				
CBC with diff	X	X	X	X
CMP	X	X	X	X
Serum hCG in women of child-bearing potential	X			
ABG	X			
Blood (30cc) for immunologic studies 	X	X (prior to treatment) and X (within 1hr after end of infusion treatment)	X (prior to treatment) and X (within 1hr after end of infusion treatment)	X 2a
Nasopharyngeal Swab (as required and based on availability)	X	X	X	X
Imaging/ Other Procedures				
12-Lead ECG	X			
CXR or CT scan 	X			

Evaluation	Screening and Informed Consent	Day 1	Day 3 (+ 1 day)	Day 7 (± 1 day) and Day 14 (± 3 days)
Clinical evaluation of endpoints 	X	X	X	X

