Study Drug Administration				
Rintatolimod/IFN regimen Administration + best available SOC		X	X	

1. Hospitalization in patients who were not inpatients at study entry; respiratory failure requiring mechanical ventilation; 14-day survival.
2. Blood (30cc) for correlative studies: On Day 1 and Day 3 prior to treatment and within 1 hour after end of infusion treatment (two draws on each of these days). Note: The combination treatment begins with IV IFN $\alpha$  followed by IV rintatolimod, with the correlative blood draw within 1 hour following IV rintatolimod as indicated above. Refer to Section 11.4. Single draws on the other days.  
2a: Follow-up visits- NOTE: In the event patient cannot tolerate treatment with all 2 days of treatment, then blood (30cc) for correlatives will be collected at time that the patient recovers from toxicities (ideally within 1 week of the last infusion).
3. Physical exam will be limited to vitals and auscultation of lungs. Vital signs (temperature, heart rate, respiratory rate, blood pressure, SaO2), body weight, and height: Height collected at baseline only.
4. NOTE: If a chest CT is ordered as standard of care prior to starting treatment, a chest x-ray is not required.
5. While every effort will be made to complete assessments, there are limitations for outpatients, including securing transport to Roswell Park. Some follow up visits will need to be done virtually, and in other cases, may be limited to viral swabs. These missed assessments or sample collections for outpatients will not be considered protocol violations.

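### Dose escalation can count a patient as DLT-free with no safety labs after the second dose, because the one draw that could fall in the Day 1–7 window may be late or skipped and no DLT-evaluability rule exists

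*Combined protocol and SAP*

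**What the plan says.** Section 10.2.2 states: "Treatment-related DLTs will be defined as the following events that occur between Day 1 to Day 7". The qualifying events are grade 3 and 4 hematologic and non-hematologic toxicities, with listed exceptions. One criterion depends on duration: "Grade 3 hematologic toxicity with exception of transient leukopenia, neutropenia, lymphopenia, thrombocytopenia without bleeding, or anemia lasting 7 days or less".

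The Main Cohort calendar (Appendix F) schedules CBC and CMP at screening, Day 1, Day 3 (+1 day), Day 7 (±1 day) and Day 14 (±3 days). Under Section 10.1 each treatment starts only "once the relevant laboratory studies have been confirmed to be within clinically acceptable ranges", so the Day 3/4 safety labs come before the second dose. The blood taken within an hour after infusion is for correlative studies.

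Footnote 5 of that calendar promises best efforts to complete assessments but adds: "Some follow up visits will need to be done virtually, and in other cases, may be limited to viral swabs". For outpatients, the resulting missed assessments are not violations.

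Section 19.2.1 runs the 3+3 "with three patients added to any dose level if we observe 1 out of 3 DLTs", and does not proceed to the next level once 2 of 3 to 6 subjects have a DLT. It staggers enrolment only until the first patient at a level has had both doses. Section 7 calls the planned Main Cohort participants evaluable without defining the term.

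**The concern.** Grade 3–4 cytopenias and liver-test elevations are found by blood tests. If no blood is drawn between the second dose and the end of the window, an asymptomatic laboratory DLT from that dose goes unseen. The error runs one way: missing labs can remove a DLT from the count but cannot add one.

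The count decides whether IFNα is escalated and which dose goes to the 10 Phase IIa patients. Section 10.2.3 itself names myelosuppression and hepatotoxicity as toxicities to watch. The Main Cohort excludes severe COVID-19 and Section 24 describes an outpatient study, so footnote 5 could apply to much of the dose-escalation group.

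**Working it through.** **The plan's own figure.** Section 19.1 gives a Phase I size of 3 to 24. One level × 3 patients = 3, and four levels × 6 patients = 24. The figure reproduces, and it leaves no room for replaced patients.

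**Visit timing.** With the second dose on Day 3 or 4:

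| Day 7 visit held on | Days after dose 2 | Inside Day 1–7? |
|---|---|---|
| Day 6 | 2 or 3 | yes |
| Day 7 | 3 or 4 | yes |
| Day 8 | 4 or 5 | no |

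The next scheduled safety labs are at the Day 14 visit (Days 11 to 17), after the window. One draw therefore carries the post-dose-2 laboratory information. One of its three permitted days lies outside the window, and footnote 5 allows it to be absent.

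**Duration criterion.** Taking the 7-day limit to govern the whole list of cytopenias and counting the onset day as day 1, duration first exceeds 7 days on onset day + 7:

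- Onset Day 1: Day 8
- Onset Day 3 or 4: Day 10 or 11
- Onset Day 7: Day 14

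No onset can be settled by Day 7. The gap between the Day 7 and Day 14 visits runs from 11 − 8 = 3 to 17 − 6 = 11 days. It exceeds 7 days in 9 of the 3 × 7 = 21 permitted pairs of visit days, so even the next scheduled labs often cannot settle the duration of an abnormality first seen at the Day 7 visit.

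**Effect on escalation (illustration).** In a 3+3, escalation follows 0 of 3 or 1 of 6 DLTs:

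P(escalate) = (1−p)³ + 3p(1−p)² × (1−p)³

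The observed rate is p_obs = p(1 − s·u·m), where s is the share of DLTs detected by laboratory tests, u the share of those visible only at the Day 7 draw, and m the share of patients without that draw. None of these inputs is in the documents. Assume p = 0.33, s = 0.5, m = 1/3.

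- All DLTs captured: p = 0.33; 0.3008 + 0.99 × 0.1350 = 0.434.
- u = 0.5: p_obs = 0.33 × (1 − 0.0833) = 0.3025; 0.3393 + 0.9075 × 0.1651 = 0.489.
- u = 1: p_obs = 0.33 × (1 − 0.1667) = 0.275; 0.3811 + 0.825 × 0.2003 = 0.546.

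Chance of escalating over a wider range of assumptions:

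| True DLT rate | none missed | 10% of DLTs missed | 25% missed | 50% missed |
|---|---|---|---|---|
| 20% | 0.71 | 0.75 | 0.81 | 0.91 |
| 33% | 0.43 | 0.50 | 0.61 | 0.78 |
| 40% | 0.31 | 0.38 | 0.49 | 0.71 |
| 60% | 0.08 | 0.13 | 0.23 | 0.49 |

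**The case against.** The strongest reply is that the Day 7 labs are scheduled (Section 11.2 and Appendix F), and that footnote 5 only settles what counts as a violation, applies to outpatients alone and opens with a commitment to complete the assessments. Symptomatic DLTs can still be recorded at a virtual visit. Toxicity of the first dose can show on the Day 3/4 labs. Section 17.4 foresees extra tests for significant abnormalities, and Sections 19.7 and 20 provide committee review. Section 2.4 reports no DLTs in earlier combination trials, though in cancer rather than COVID-19. All of this stands and limits the problem. None of it supplies a rule for a patient whose post-dose-2 labs do not exist.

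A reader might also infer more than the text supports:

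- *Patients without labs are counted as DLT-free.* Section 19.2.1 does not say so. It leaves the matter undefined, which permits that count.
- *A grade 4 value found on Day 8 is discarded.* Section 10.2.2 dates the event, not the draw. The two windows disagree, but no text orders such a value to be ignored.
- *The duration criterion makes the definition unworkable.* It can be read as onset by Day 7 with duration judged later. Day 14 labs are scheduled and adverse-event follow-up continues (Section 17.6.2). No text states that reading or makes the dose-level decision wait for it. Only the listed cytopenias are exempt, and thrombocytopenia only without bleeding.
- *Pancreatic-enzyme DLTs would be lost with the draw.* The calendar lists no amylase or lipase, and asymptomatic grade 4 elevations of either are exempt.
- *Escalation is inflated to 78%.* With p = 0.33 and half of DLTs laboratory-detected, that needs every laboratory DLT to be visible only at the Day 7 draw and every patient to miss it.

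**Conclusion.** The point holds as a gap in the escalation rules, and it should be fixed. Stated provisions let a dose level be cleared without the tests that define laboratory DLTs after the second dose, and the bias favours escalation. It is confined to laboratory-defined toxicity not already visible on Day 3/4.

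Under the illustrative inputs the chance of escalating past a level with a 33% DLT rate rises from 43% to about 49%, or to 55% if no laboratory DLT shows before the Day 7 draw. The size rests on assumed values for the DLT rate, the laboratory share and the missing share; the direction does not. Because the documents do not show how often labs would be missed, they do not support calling the escalation invalid.

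**What to change.** 1. In Section 19.2.1, define a DLT-evaluable patient as one who has had a DLT or who has the scheduled CBC/CMP after the second dose. Replace other patients, so that they do not count toward the 3 or 6.
2. Exclude the Day 7 CBC/CMP of dose-escalation patients from footnote 5. A local laboratory draw is acceptable.
3. Reconcile the Day 1–7 window in Section 10.2.2 with the Day 7 (±1) visit and with the 7-day duration criterion, and state when a dose level is complete for the escalation decision. The choice of window and duration rule is the sponsor's.

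The cost is a short amendment, occasional local draws and some replaced patients. The range of 3 to 24 would then refer to evaluable patients, with enrolment higher by the number replaced. Depending on how item 3 is resolved, decisions may be delayed, perhaps more than occasionally, since Table 2 expects transient neutropenia.
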